8 STUDY ASSESSMENTS AND PROCEDURES

8.1 ENDPOINT AND OTHER NON-SAFETY ASSESSMENTS

Patient and caregiver participants are asked to complete baseline surveys and follow-up questionnaires at 12 and 24 weeks by phone. Baseline surveys are collected by the trained study coordinator after consent and prior to randomization. For the baseline, 12-week, and 24-week surveys, a blinded data collector will call the participant at home to complete.

- There is a 14-business day window on either side of the due date for participants to complete their follow-up questionnaires. Participants can complete study questionnaires within a 28-business day timeframe from 14 days before the time point to 14 days after.
- Participants have 30 business days to complete baseline questionnaires after completing informed consent. Caregivers will complete follow-up questionnaires as per the timeline (i.e., even if the patient baseline is completed three weeks after the caregiver baseline, both parties will complete the first follow-up questionnaire 12 weeks after the patient baseline questionnaire completion date).
- Data collected outside of these time points will not be evaluable.
- To minimize missing data, a postcard reminder of an upcoming questionnaire window will be sent 1-2 weeks prior to opening of the data collection window (**Survey Reminder Postcard: Section 12.4.9**). Data collectors will also begin calling participants within 14 days of the study window to ascertain if they would like to complete questionnaires by phone or web.

A screening and tracking log will be used to track whose follow-up questionnaires are due, and when the windows open and close.

If a participant refuses to complete a questionnaire or says it is too much, attempts will be made to try to have them at least complete the mood and quality of life measures (patient and caregiver).

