4 STUDY DESIGN

4.1 OVERALL DESIGN

This hybrid type-1 effectiveness-implementation pilot RCT is designed to answer the question “Is EPIC feasible and acceptable in older adults with COPD and their caregivers?”. The primary aims are to assess implementation feasibility and acceptability (intervention and trial) over 24 weeks (*Aims 1 and 2*). We will also explore means and variance estimates of the secondary GeriPal outcomes to guide future R01 development (*Exploratory Aim*). We will recruit 30 dyads of older adults with moderate to very severe COPD (FEV₁ <80%) from pulmonary clinic and their caregivers. Half of the dyads will be randomized to EPIC + usual care (n=30 patients and n=30 caregivers). To reflect current clinical realities and uphold the pragmatic design, the other half of dyads (n=30 patients and n=30 caregivers) will be assigned to usual care alone (**see Section 1.2 for Design Schema**). Participants will complete assessments at enrollment (T1), week 12 (T2), and week 24 (T3). The T2 assessment captures the short-term outcomes of the most intensive part of the intervention. The T3 assessment will capture the long-term outcomes of the intervention. Assessments will be administered by phone and entered into the REDCap database system by a data collector blinded to study arm. For non-responders after 2 weeks, assessments will be additionally attempted by the data collector.

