5.4 SCREEN FAILURES

Screen failures are defined as participants who consent to participate in this study but are not subsequently randomized. Reasons for screen failure include:

- 1) Failure of the patient and/or the caregiver to complete baseline measures within 14 days of signing informed consent.
- 2) Death of the patient and/or caregiver prior to completing baseline measures.

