6.1.2 SUMMARY OF PROTOCOL

Training of Study Team Members

The intervention requires two nurse coaches who are hired and trained by the PI and co-investigator, [name]. Advanced training specific to EPIC consists of independent readings, review of all intervention materials and the protocol, in-depth discussions on COPD and its management, and thorough review of the protocol. The PI will chair weekly nurse coach meetings to review progress and intervention receipt.

Enrollment Procedures.

All agreeable and eligible patient participants who consent to participate in the study complete an intake form that includes demographic data (all participants), clinical data (patients only), and symptom surveys (patients and caregivers). We are measuring Life-Space mobility, quality of life, caregiver burden, functional status, mood symptoms, loneliness, and cognitive impairment. If time allows for participants, baseline surveys will be completed immediately after consent. If time does not permit in the patient's schedule, the intake surveys will be completed by telephone at a mutually-agreed upon time. Agreeable and eligible caregivers who consent to participate in the study will also be provided a short intake form of their demographic and background information as well as intake symptom surveys. If the time does not permit in the caregiver's schedule, the intake surveys will be completed by telephone at a mutually agreed upon time.

Summary of Randomization Procedures.

Randomization will take place after the informed consent and intake are obtained from both the patient and the caregiver. We will randomize 30 patient-caregiver dyads in a 1:1 fashion to the study arms: 1) EPIC + usual care (n=15 dyads); and 2) usual care alone (n=15 dyads). A randomization table will be generated to allocate all 30 dyads to the study arms. Randomization procedures will be supervised by the biostatistician, [name] (Co-I and trial statistician) at UAB. The randomization scheme will be executed using an Excel randomization table and recorded in REDCap. The study coordinator will complete the randomization procedure and record study group in REDCap. The study coordinator will inform the usual group participants of their group assignment and will also alert the interventionists to initiate intervention activities with the intervention group participants.

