6.1.3 SUMMARY OF TRIAL PROCEDURES

Control Arm

The control arm of the study will be usual care for COPD in pulmonary clinic (**Table 1**) which includes symptom management, inhalers, advanced COPD therapies as needed, illness education, informal tobacco cessation counseling, supplemental oxygen testing, and referral to cardiopulmonary rehabilitation and other services as appropriate per the clinician.

Table 1. Control Arm Procedures and Timeline (Usual Care)					
Study Week	Type of Session	Investigator	Participant	Estimated Participant Time (minutes)	Description
1	In-person/ Phone	Coordinator	Patient + Caregiver	60	Study introduction, informed consent, intake surveys
2-24	N/a	N/a	Patient + Caregiver	N/a	Usual COPD care
12	Phone	Data Collector	Patient + Caregiver	60	Midpoint surveys
24	Phone	Data Collector	Patient + Caregiver	60	Exit surveys
24	Phone	Coordinator	Patient + Caregiver	30	Post-intervention acceptability survey Post-intervention feedback interview

Intervention Arm

Dyads randomized to the intervention arm will receive EPIC along with usual care (**Table 2**). EPIC includes weekly, telephone-based palliative care nurse coaching aided by the manualized curriculum, *“Charting Your Course (CYC): An Intervention for Patients with COPD and their Caregivers”*. This is followed by brief telephone follow-up calls monthly until study completion. Patient participants are also scheduled for a visit with the Supportive Care Clinic at The Kirklin Clinic, where trained clinicians complete a comprehensive palliative care assessment, virtually if preferred. Current intervention materials for EPIC and nurse coach CYC phone scripts are being edited and refined. Final copies of all intervention materials and phone scripts will be submitted as an amendment at a later date.

Table 2. Intervention Arm Procedures and Timeline (EPIC + Usual Care)					
Study Week	Type of Session	Investigator	Participant	Estimated Participant Time (minutes)	Description
1	In-person/ Phone	Coordinator	Patient + Caregiver	60	Study introduction; consent; intake surveys
2-12	In-person/ Virtual	N/A	Patient + Caregiver	60	Supportive Care Clinic visit; comprehensive palliative care assessment
3	Phone	Nurse coach	Patient + Caregiver	45	CYC Session 1: Problem solving
4	Phone	Nurse coach	Patient +	45	CYC Session 2: Self-care management

			Caregiver		
5	Phone	Nurse coach	Patient + Caregiver	45	CYC Session 3: Assessing, prioritizing, and managing symptoms

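### Follow-up is counted from the patient's baseline but randomization waits for both intakes, so a caregiver who finishes later shortens the time from randomization to T2 and T3

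*Combined protocol and SAP*

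**What the plan says.** Section 8.1 fixes the first follow-up for the dyad: "both parties will complete the first follow-up questionnaire 12 weeks after the patient baseline questionnaire completion date". Its only illustration is a patient who finishes last: "even if the patient baseline is completed three weeks after the caregiver baseline". The rule is written for the first follow-up; I take week 24 to run on the same clock, since nothing suggests another.

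Section 6.1.2 sets a different trigger for randomization: "Randomization will take place after the informed consent and intake are obtained from both the patient and the caregiver". Only then does the coordinator act on allocation; he or she "will also alert the interventionists to initiate intervention activities with the intervention group participants". No section ties T2 or T3 to the randomization date.

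The time allowed for baseline is given twice, differently. Section 8.1: "Participants have 30 business days to complete baseline questionnaires after completing informed consent". Section 5.4 lists as a screen failure: "Failure of the patient and/or the caregiver to complete baseline measures within 14 days of signing informed consent". Both limits run from consent, and no limit is stated on the gap between the two members' consents.

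Section 4.1 gives the purpose of the 12-week assessment: "The T2 assessment captures the short-term outcomes of the most intensive part of the intervention". On the monthly calls, section 6.1.3 says of the weekly coaching: "This is followed by brief telephone follow-up calls monthly until study completion".

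**The concern.** The follow-up clock and the randomization trigger coincide only if the patient finishes baseline last or both finish together. That is the order in the section 8.1 example, where no follow-up time is lost. In the reverse order the clock is already running while the dyad waits to be randomized.

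The reverse order is plausible. Under section 10.1.1 the patient is screened and consented first, and the caregiver is approached afterwards with the patient's permission. Section 6.1.2 has baseline surveys done straight after consent when time allows, so a patient may finish before the caregiver has consented.

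At stake are the 12- and 24-week means and variances of the LSA and the other secondary outcomes, which are to inform the R01. If some EPIC dyads are measured after less of the programme than others, those estimates mix different amounts of exposure, and T2 may no longer serve the purpose given in section 4.1.

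**Working it through.** **Inputs.** T2 and T3 are due 12 and 24 weeks after the patient's baseline (8.1). Randomization follows the later intake (6.1.2). The baseline limit is 14 days = 2 weeks (5.4) or 30 business days = 30/5 = 6 weeks (8.1). The follow-up window is 14 business days = 14/5 = 2.8 weeks either side (8.1), so the T2 window opens at 12 − 2.8 = 9.2 weeks and the T3 window at 24 − 2.8 = 21.2. Table 2 puts CYC Sessions 1 to 6 in study weeks 3 to 8 and the monthly calls in weeks 12 to 24.

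**Assumptions.** Both members consent on the same day, the patient completes baseline that day, and randomization occurs on the day of the caregiver's baseline. Table 2 spacing is kept after the delay. Calls fall in study weeks 12, 16, 20 and 24. Table 2 labels consent and intake as week 1, so week labels can be read as weeks since baseline (reading A) or as label minus 1 (reading B).

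**The plan's own schedule, no lag.** Session 6 falls at week 8 (A) or 7 (B). All six sessions come before the T2 window opens, and all four calls by the T3 due date. The plan is coherent when the lag is zero.

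**With lag L weeks.** Time from randomization to T2 = 12 − L, and to T3 = 24 − L. On the patient's clock, Session 6 falls at 8 + L (A) or 7 + L (B), and the calls likewise move by L. Where two figures are shown, they are A; B.

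| Lag L | Randomization to T2 | Randomization to T3 | Session 6, patient's clock | Patient sessions by T2 due date | Patient sessions when T2 window opens | Calls by T3 due date |
|---|---|---|---|---|---|---|
| 0 | 12 | 24 | 8; 7 | 6; 6 | 6; 6 | 4 |
| 2 (14 days) | 10 | 22 | 10; 9 | 6; 6 | 5; 6 | 3 |
| 3 | 9 | 21 | 11; 10 | 6; 6 | 4; 5 | 3 |
| 6 (30 business days) | 6 | 18 | 14; 13 | 4; 5 | 1; 2 | 2 |

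Example, L = 6, reading A: sessions fall at weeks 9, 10, 11, 12, 13 and 14, so four are delivered by week 12 and one by week 9.2. Calls fall at weeks 18, 22, 26 and 30, so two come by week 24. The caregiver's four sessions (weeks 9 to 12) are complete by the T2 due date on either reading.

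**Longer spacing.** Section 6.1.1 allows sessions every 1 to 2 weeks. At two-week spacing Session 6 falls at 3 + 5 × 2 = 13 (A) or 12 (B) with no lag at all. With L = 6 it is at week 19 or 18, still before the T3 window opens at 21.2.

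**Effect on the arm mean.** With 15 dyads per arm, each lagging EPIC dyad takes L/15 weeks off mean exposure at T2 and T3: 2/15 = 0.13 weeks at L = 2 and 6/15 = 0.4 weeks at L = 6. The documents do not say how many dyads would lag, so the total reduction lies between 0 and L weeks.

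**After the change.** With due dates counted from randomization, T2 and T3 are 12 and 24 weeks after it for every dyad. On weekly spacing and reading A, Session 6 (week 8) then comes 4 weeks before T2 is due and 9.2 − 8 = 1.2 weeks before its window opens.

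**The case against.** Several points against this are sound.

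- A reader might infer that T2 and T3 fall before the intervention has been delivered. The documents do not support that. All core sessions precede T3 at every lag up to 6 weeks. On weekly spacing, all six precede the T2 due date at lags of 2 or 3 weeks. Only the 6-week case puts T2 on its due date before Session 6, and with same-day consents that case exists only if section 8.1 prevails over section 5.4. This limits the size of the problem but does not remove the mismatch: even at 2 weeks the interval is short by the full lag, and consents given on different days could lengthen it.
- A reader might infer bias between arms. The lag arises before randomization and the rule is the same in both arms, so there is no differential timing.
- A reader might infer that the primary session counts are depressed. Completion is logged in REDCap and is not defined by T2 or T3, and section 6.1.3 has coaches call monthly after the last session. That calls stop at the T3 survey is inferred by joining the 6.1.3 wording to the definition of a completed participant in section 4.4. If they do stop, and if the 10 and 8 components in section 3 are sessions plus four calls, the 6-week maxima are 6 + 2 = 8 and 4 + 2 = 6. These equal the cut-offs for the overall average, so lag alone cannot make the criterion fail. A T3 at the late edge (24 + 2.8 = 26.8) admits a third call at L = 6. With no lag, a T3 at the early edge (21.2) already misses the fourth. The effect on counts is secondary.
- Section 8.1 also describes its window as 14 days. With calendar days the T2 window opens at week 10, and early-edge losses are smaller: at L = 3, five (A) or six (B) sessions precede it.
- Frequency is unknown. Section 5.5 screens both members at the same time, Tables 1 and 2 put both intakes in week 1, and section 1.4 puts baseline and randomization in one column.
- Anchoring on the patient's baseline keeps that patient's baseline-to-follow-up interval constant, which is a defensible aim. The price is variable time since randomization, which matters more for a T2 tied to a phase of the intervention.

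**Conclusion.** The mismatch is real, and its consequence is modest and conditional. A caregiver who completes baseline after the patient shortens the time from randomization to T2 and T3 by the lag. With same-day consents this is up to 2 weeks under section 5.4 (10 and 22 weeks) and up to 6 under section 8.1 (6 and 18 weeks). At the 6-week limit, T2 is due with four or five of six patient sessions delivered, contrary to its purpose in section 4.1, and about two of four monthly calls fall after the T3 due date. Because the gap between consents is not limited, longer lags are possible.

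What follows is shorter and more uneven exposure in the EPIC arm, hence some dilution and extra noise in exploratory estimates. The documents give no basis for putting this in LSA points. The session results rest on weekly spacing kept after the delay, randomization on the day of the second baseline, and week 24 sharing the week 12 anchor. The change is worth making because it costs little.

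**What to change.** In section 8.1, count the 12- and 24-week due dates and their windows from the date of randomization, for both dyad members and in both arms. Drive the reminder postcards and the tracking-log dates from that same date. Leave consent and intake in Tables 1 and 2 as activities before randomization, and do not recount that row. Reconcile the baseline deadlines in sections 5.4 and 8.1, and say whether the gap between the two consents is limited.

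The cost is one sentence in section 8.1, one date field behind the tracking log, and the reconciliation. The downside is that in lagging dyads the patient's baseline-to-follow-up interval lengthens by the lag. At 2 weeks it becomes 14 and 26 weeks. At 6 weeks it becomes 12 + 6 = 18 and 24 + 6 = 30 weeks, which is a further reason to settle the baseline deadline at the same time.

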8.2 SAFETY ASSESSMENTS

N/A

8.3 ADVERSE EVENTS AND SERIOUS ADVERSE EVENTS

8.3.1 DEFINITION OF ADVERSE EVENTS

Very broadly, an adverse event is any untoward event occurring to a participant while enrolled on a clinical trial, which may or may not be related to the intervention and/or study procedures.

8.3.2 DEFINITION OF SERIOUS ADVERSE EVENTS

Broadly, an adverse event is any untoward event occurring to a participant while enrolled in a clinical trial, which may or may not be related to the intervention and/or study procedures. In our experience of providing palliative care interventions using highly experienced palliative care nurse coaches, the risk of emotional distress is quite low. Furthermore, the intervention offers participants the opportunity to reflect upon strengths and resilience, and participants often express gratitude for the chance to share their experiences. This trial is considered minimal risk as there are not expected to be any serious adverse events related to the study intervention or procedures, and we are not collecting blood samples or prescribing new medications in this study. While death and hospitalization are anticipated of patient participants, these are due to medical illness rather than the study intervention.

8.4 UNANTICIPATED PROBLEMS

This protocol uses the definition of Unanticipated Problems as defined by the Office for Human Research Protections (OHRP). OHRP considers unanticipated problems involving risks to participants or others to include, in general, any incident, experience, or outcome that meets all of the following criteria:

- Unexpected in terms of nature, severity, or frequency given (a) the research procedures that are described in the protocol-related documents, such as the Institutional Review Board (IRB)-approved research protocol and informed consent document; and (b) the characteristics of the participant population being studied;
- Related or possibly related to participation in the research (“possibly related” means there is a reasonable possibility that the incident, experience, or outcome may have been caused by the procedures involved in the research); and
- Suggests that the research places participants or others at a greater risk of harm (including physical, psychological, economic, or social harm) than was previously known or recognized.

8.5 REPORTING OF ADVERSE EVENT AND UNANTICIPATED PROBLEMS

A summary of anticipated serious adverse events (i.e. death and hospitalizations) will be reported to the Safety Officer and NIA PO quarterly. The PI will report unanticipated problems to the reviewing IRB, SO and the NIA PO within 48 hours. The report will include the following information:

- Protocol identifying information: protocol title and number, PI's name, and the IRB project number
- A detailed description of the event, incident, experience, or outcome
- An explanation of the basis for determining that the event, incident, experience, or outcome represents an UP
- A description of any changes to the protocol or other corrective actions that have been taken or are proposed in response to the UP

8.5.1 REPORTING UNANTICIPATED PROBLEMS TO PARTICIPANTS

N/A

9 STATISTICAL CONSIDERATIONS

9.1 HYPOTHESES

Aim 1: Explore feasibility and acceptability of the EPIC intervention.

Hypothesis 1. Participants can feasibly complete the EPIC intervention (>80% of intervention components completed) and report high acceptability (*primary outcome*).

Aim 2: Determine the feasibility of a hybrid-type 1 effectiveness-implementation trial in older adults with COPD and their caregivers.

Hypothesis 2. It is feasible and not burdensome to recruit, randomize, retain, and survey older adults with COPD and their caregivers (*primary outcome*).

Exploratory Aim: Explore mean and variance estimates on Life-Space mobility by the UAB Life Space Assessment and other GeriPal outcomes to inform a fully-powered trial (*secondary outcome*).

9.2 SAMPLE SIZE DETERMINATION

As this is a feasibility study, sample size is justified based on the measurement precision of LSA parameters for a larger study. Using a sample size of 24 patients (48 participants including patients and caregivers) and 12 patients per study arms, we can estimate the 95% confidence interval of mean LSA with a margin of error of 14.3. This margin of error is equal to 0.567 standard deviation when we observe a reference standard deviation for the LSA of 25.2 from a general population of older adults. This sample size also includes an estimated 20% attrition rate from a sample of 30 dyads (or 60 patient and caregiver participants), which is consistent with palliative care trials.

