9.4 STATISTICAL ANALYSES

9.4.1 GENERAL APPROACH

Overall considerations. We will use an intention to treat approach for all analyses. That is, all participants will be included in their respective assigned conditions, regardless of their degree of participation in the study. [name] (Co-I; Statistician) and the data analyst will lead and conduct the analysis. The data analyst and project staff will perform data cleaning and validation throughout the study. Primary data analysis will begin with descriptive statistics for baseline characteristics and outcomes. We will examine balance between study groups with respect to baseline characteristics using effect sizes such as the standardized mean difference for numerical variables and Cramer's V for categorical variables. Conceptually relevant baseline factors showing non-trivial imbalances between groups will be then used as adjusting covariates in the longitudinal group comparisons. Distributional assumptions will be examined and, when appropriate, we will employ inferential and modeling

procedures robust to distributional assumptions such as normality. We will calculate and present means, variances, and ranges of the LSA and other secondary outcomes at baseline, 12 weeks, and 24 weeks. We will use the latest versions of SAS and R for all analyses and reports.

Handling of missing data. We will examine patterns of missing data, and whether baseline characteristics are associated with dropout. Conceptually relevant baseline factors predictive of dropout will then be used as adjusting covariates in the longitudinal group comparisons. Mixed-effect modeling techniques and covariate adjustment will reduce the impact of missing data, as the missingness is not assumed completely at random (MCAR) but conditionally (on the covariates) at random (i.e., MAR, a milder assumption).

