10.1.7 SAFETY OVERSIGHT

This project will involve enrolling 30 older adults with COPD and 30 caregivers into a pilot randomized controlled trial. After signing consent, participants will complete a baseline surveys. Dyads randomized to the intervention arm will engage in the EPIC intervention delivered over telephone by trained palliative care nurse coaches. The interventions and assessments are not invasive and do not involve pharmacological agents. The informed consent process, the recruitment process, and the timeliness and quality of the data will be monitored by the principal investigator, the Institutional Review Board, and a Safety Officer (SO).

The SO will provide safety oversight and be composed of individuals with the appropriate expertise, including oncology, medicine, nursing, and clinical trials. The SO will be independent from the study conduct and free of conflict of interest. The SO will review quarterly safety reports from the PI to assess safety. The SO will provide its input to the IRB.

The SO has an established procedure of operation and guidelines for determining the methods and frequency for study review. Below is the table that guides the risk assessment for this study. Based on our SO established guidelines, the proposed study's score of five on the 10-point scoring system indicates that the principal monitor for the study will be the PI ([name]), and he will present the SO with a summary of the accumulated data and safety information during an annual review for each year of the study.

Tasks related to patient safety will include [name] assessment of potential risks associated with study recruitment and participation, as well as the design and implementation of procedures to minimize these risks should they arise. Additionally, [name] and the Co-Investigators will implement a system to document adverse events should they occur. The IRB Institutional Review Board currently has procedures in place for reporting adverse events and those protocols will be followed for the current study. This risk monitoring will be reviewed on a regular basis and will be modified as needed.

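### The LSA margin of 14.3 in Section 9.2 treats the SD as known; with the SD estimated it is 15.1 or 16.0. Separately, Section 4.1 doubles each arm.

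*Combined protocol and SAP*

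**What the plan says.** Section 9.2 bases the sample size on how precisely the LSA can be measured. It takes 24 evaluable patients, 12 per arm, after 20% attrition from 30 dyads, and states: "we can estimate the 95% confidence interval of mean LSA with a margin of error of 14.3". It equates this margin to 0.567 SD, "when we observe a reference standard deviation for the LSA of 25.2 from a general population of older adults". It names no formula, does not say whether the margin is for one arm or for all patients, and does not say whether the SD is each arm's own or pooled.

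Other sections make the LSA variance something the trial will estimate. The exploratory aim in Section 9.1 is to "Explore mean and variance estimates on Life-Space mobility by the UAB Life Space Assessment". Section 9.4.1 adds: "We will calculate and present means, variances, and ranges of the LSA and other secondary outcomes at baseline, 12 weeks, and 24 weeks".

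On arm size, Section 4.1 recruits 30 dyads in total and then says: "Half of the dyads will be randomized to EPIC + usual care (n=30 patients and n=30 caregivers". For the control arm it says: "the other half of dyads (n=30 patients and n=30 caregivers) will be assigned to usual care alone". Section 6.1.2 gives the allocation as "1) EPIC + usual care (n=15 dyads); and 2) usual care alone (n=15 dyads". Section 10.1.7 gives the total: "This project will involve enrolling 30 older adults with COPD and 30 caregivers into a pilot randomized controlled trial". The synopsis (1.1), Section 5.5 and Section 9.2 agree with that total.

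**The concern.** There are two independent points.

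The first is the margin. A 95% interval built with 1.96 is exact only if the SD is known. Here the SD is borrowed from a general population of older adults, while the trial enrols patients with moderate to very severe COPD who also have severe breathlessness, a hospitalization in the prior year, or supplemental oxygen. The plan intends to learn the LSA variance in these patients. With 12 patients per arm the difference between the normal and t quantiles is visible, so the stated precision is better than the trial can deliver at that sample size. This margin is the only quantitative justification of the sample size. The variance is also a named target for planning the larger study, yet no precision is given for it.

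The second is the arm size. Section 4.1 is the main design paragraph, and it contradicts its own total. Taken literally, it describes a trial twice as large.

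**Working it through.** **Inputs.** From Section 9.2: 95% confidence, SD 25.2, 24 evaluable patients, 12 per arm. From Sections 4.1 and 6.1.2: 30 dyads, allocated 1:1.

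**Reproducing the plan's figure.** The half-width for one arm's mean, with the SD known, is z × SD/√n:

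- 1.96 × 25.2/√12 = 14.26, which rounds to 14.3.
- 14.3/25.2 = 0.567, which matches the stated SD units. Without rounding the margin first, 1.96/√12 = 0.566.

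**Other constructions from the plan's numbers.**

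| Construction | Half-width |
|---|---|
| One arm, n = 12, t with 11 df | 16.01 |
| One arm, n = 12, pooled SD, t with 22 df | 15.09 |
| All 24 patients, z | 10.08 |
| All 24 patients, t with 23 df | 10.64 |
| Difference between arms, 12 per arm, z | 20.16 |
| Difference between arms, 12 per arm, t with 22 df | 21.34 |

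None of these gives 14.3. A between-arm difference with 24 patients in each arm would also give 14.26 by z, because √(2/24) = √(1/12). That would need 48 patients, and the plan has 24. So 14.3 is a one-arm, known-SD figure.

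**Margin with the SD estimated, observed SD 25.2.** The half-width is t × SD/√12:

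- Arm's own SD, 11 df, t = 2.201: 2.201 × 25.2/√12 = 16.01, or 0.635 SD. Ratio to the plan: 16.01/14.26 = 1.12.
- SD pooled across arms, 22 df, t = 2.074: 2.074 × 25.2/√12 = 15.09, or 0.599 SD. Ratio to the plan: 15.09/14.26 = 1.06.

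Put the other way, an interval using 1.96 with an estimated SD covers about 92.4% (11 df) or 93.7% (22 df), not 95%.

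**Precision of the SD.** The 95% interval is SD × √(df/χ²), with the upper and lower 2.5% points of χ²:

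- 22 df (12 per arm, pooled): 19.5 to 35.7.
- 29 df (baseline SD from all 30 patients): 20.1 to 33.9.

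**Arm size.** 30 dyads / 2 = 15 dyads per arm, that is, 15 patients and 15 caregivers. Thirty of each per arm would need 60 dyads. The attrition step confirms the total: 24/(1 − 0.20) = 30 patients, and 15 × 0.80 = 12 per arm, the number used in Section 9.2.

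**The case against.** The best defence is that 14.3 is not a slip. It is correct under the normal formula, its inputs are disclosed, and a normal-quantile planning margin is a common approximation. Because no formula is stated, the known-SD reading is inferred. All of this is true. The inference is firm, however, since no t-based version at 12 per arm gives 14.3.

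A second argument concerns baseline. LSA means will also be reported before any attrition, with 15 patients per arm. There the t-based margins are 13.96 (own SD, 14 df) and 13.33 (pooled, 28 df), both below 14.3. This stands as a limit on the criticism: the stated precision is too favourable for means based on 12 completers per arm, not for baseline arm means. It does not rescue the figure, because Section 9.2 states it for 12 per arm.

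A third argument is that little depends on it. No precision target is set, the primary outcomes are feasibility and acceptability, and Section 9.4.3 lists descriptive summaries of the secondary outcomes. Uncertainty in the SD also matters more than the choice of quantile: with the pooled multiplier 2.074/√12 = 0.599, an SD of 19.5 gives a margin of 11.7 and an SD of 35.7 gives 21.4. This stands, and it is why the point is modest. It also shows why an interval for the SD would be informative, although adding one is optional.

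On Section 4.1, a reader could recover the intended size from the 30 dyads in the same paragraph and from Section 6.1.2. That lowers the practical risk, but the contradiction remains.

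**Conclusion.** Both points hold.

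At the sample size Section 9.2 states, the 95% margin for one arm's mean LSA is 15.1 with a pooled SD or 16.0 with the arm's own SD, not 14.3. The shift is 0.8 to 1.7 LSA points, or 6% to 12%. This assumes an observed SD of 25.2 and exactly 12 evaluable patients in each arm; the pooled figure also assumes a common SD in the two arms. The sample size of 30 dyads is not invalidated, because the plan sets no precision target and no primary conclusion depends on the margin.

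Section 4.1 overstates each arm by a factor of two against its own total and against Section 6.1.2. This error does not enter the 14.3.

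Both passages should be corrected. The impact is modest, but one is the sole numerical basis for the sample size and the other is the main statement of the design.

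**What to change.** In Section 9.2, state that the margin is for one arm's mean with 12 evaluable patients, based on the t distribution. Give it as 16.0 (0.635 SD, 11 df) if each arm's own SD is used, or as 15.1 (0.599 SD, 22 df) if the SD is pooled across arms, and say which applies.

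Optionally, because the variance is a named target, add the 95% interval for an SD of 25.2 with its degrees of freedom: 19.5 to 35.7 at 22 df, or 20.1 to 33.9 at 29 df for the baseline SD from all 30 patients.

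In Section 4.1, change the count for each arm to 15 patients and 15 caregivers, in both places.

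The cost is wording only: no extra patients and no change to the design or analysis. The stated precision becomes 6% to 12% less favourable.
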